Objective		Endpoint
		
 
ECGs.
 
LVEF as measured by echocardiogram.
 
NT-proBNP.
 
For participants testing positive for SARS-CoV-2 (by nucleic acid or serology test) during the intervention and follow-up periods, the number and proportion of participants with COVID-19 AEs/SAEs and the proportion asymptomatic.
 

		Number of participants seropositive for SARS-CoV-2 at end of study who were seronegative at randomization visit.

Table 5 Objectives and Endpoints

Objective	Endpoint
CCI	

**Objectives and Endpoints** Table 5

CCI
Exploratory Sub-study
CCI

AstraZeneca

```
AE = Adverse event; CCI
                                                                                         AESI = Adverse
event of special interest; AO = Airwave oscillometry; AX = Area of reactance; BCSS = Breathlessness, cough
and sputum scale; BD = Bronchodilator;
COPD = Chronic obstructive pulmonary disease; CompEx = Composite Exacerbations;
COVID-19 = Coronavirus disease 2019;
                                                              CT = Computed tomography;
                                                  ECG = Electrocardiogram; E-RS:COPD = Evaluating
Respiratory Symptoms of COPD; FEV1 = Forced expiratory volume 1 second; FVC = Forced vital capacity;
IL = Interleukin; LVEF = Left ventricular ejection fraction; CCI
NT-proBNP = N-terminal pro-brain natriuretic peptide; PD = Pharmacodynamics; CCI
                         PK = Pharmacokinetic; R5 = Resistance at 5Hz; R20 = Resistance at 20 Hz;
SAE = Serious adverse event; SARS-CoV-2 = severe acute respiratory syndrome coronavirus 2;
SGRQ = St. George's Respiratory Questionnaire; CCI
                                                                                           VAS = Visual
analogue scale.
```

AstraZeneca

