AO = Airwave Oscillometry; AX = Area of reactance; BCSS = Breathlessness, cough and sputum scale; COPD = Chronic obstructive pulmonary disease; COPDCompEx = COPD Composite Exacerbations; E-RS:COPD = Evaluating Respiratory Symptoms of COPD; PK = Pharmacokinetic; R5 = Resistance at 5 Hz; R20 = Resistance at 20 Hz; SGRQ = St. George's Respiratory Questionnaire; VAS = Visual analogue scale.

Objectives	Endpoints
CCI	
-	
-	
-	

Objectives	Endpoints
CCI	
CCI	

Table 4Safety objectives and associated endpoints

Objective	Endpoint
To assess the safety and tolerability of MEDI3506	During the intervention and follow-up periods:
compared with placebo in participants with COPD	• AEs, SAEs, AESIs.
and chronic bronchitis.	• Vital signs.
	• Clinical chemistry, haematology, and urinalysis.
	• ECGs.
	• LVEF as measured by echocardiogram.
	• NT-proBNP.
	
 
For participants testing positive for SARS-CoV-2 (by nucleic acid or serology test),
 

Objective	Endpoint
	during the intervention and follow-up periods, the number and proportion of patients with COVID-19 AEs/SAEs and the proportion asymptomatic.
	• Number of participants seropositive for SARS-CoV-2 at end of study who were seronegative at randomization visit.

AE = Adverse event; AESI = Adverse event of special interest; COPD = Chronic obstructive pulmonary disease; COVID-19 = Coronavirus disease 2019; ECG = Electrocardiogram; LVEF = Left ventricular ejection fraction; NT-proBNP = N-terminal pro-brain natriuretic peptide; SAE = Serious adverse event; SARS-CoV-2 = severe acute respiratory syndrome coronavirus 2.

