#### Adverse events of special interest

The following AESIs will be particularly monitored in this study:

- Hepatic function abnormality meeting the definition of HL as described in CSP Section 8.3.7.
- Serious hypersensitivity (including Type 1 to 4 hypersensitivity reactions), for example anaphylaxis and severe allergic reactions, and immune complex disease.
- Injection site reactions (ISR).
- Cardiac events (including angina or myocardial infarction, congestive heart failure, symptomatic atherosclerotic vascular disease, cor pulmonale, or arrhythmia).
- Serious infections (including opportunistic infections and viral reactivations), for example herpes simplex virus/varicella zoster virus, Epstein Barr virus/cytomegalovirus, TB, and all other opportunistic infections listed in the Guidelines for the Prevention and Treatment of Opportunistic Infections in HIV Infected Adults and Adolescents: Recommendations from the Centers for Disease Control and Prevention, the National Institutes of Health, and the HIV Medicine Association of the Infectious Diseases Society of America (NIH 2019).
- Gastrointestinal AEs
- Malignancy

AEs will be assigned to a specific category based on investigator's judgement, using a checkbox on the AE CRF page. In addition, standardized MedDRA queries (SMQs) will be used when possible, and a selection of HLTs, SOCs and/or PTs will be used to represent other situations, to perform a cross-check with eCRF categories. A comprehensive list will be provided by the patient safety team prior to any study delivery.

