#### **COVID-19 related AEs and SAEs**

AE or SAE will be considered as related to COVID-19 if a participant has been tested positive for SARS-CoV-2 (by nucleic acid or serology test), during the intervention and follow-up periods and had an AE or SAE associated with COVID-19 based on the COVID-19 SMQ.

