- Time from first IP administration to onset of AE (days) as derived in Section 3.1.8.6
- Treatment period
- Time from last IP administration to death (days) as derived in Section 3.1.8.8
- Time from first IP administration to death (days) as derived in Section 3.1.8.9
- Received treatment for AE
- Reasonable possibility AE caused by IP

The number of SAEs by SOC and PT term will be summarised by study intervention group. The number and percentages of participants with SAEs by SOC and PT term will be summarised by study intervention group. Key participant information for participants experienced SAEs will be produced using following information:

- Study intervention group
- Participant identifier
- Sex
- Age (years)
- Event term as reported by the investigator
- PT term
- Time from first IP administration to onset of AE (days) as derived in Section 3.1.8.6

- Time from last IP administration prior to AE start date, calculated for AEs starting after the discontinuation of the IP.
- Time from start of IP administration to becoming serious
- Outcome
- Action taken with IP
- Reasonable AE caused by IP

The number and percentages of participants with AEs leading to discontinuation of investigational product by SOC and PT term will be summarised by study intervention group. Key participant information for participants experienced AEs leading to discontinuation of IP will be produced using following information:

- Study intervention group
- Participant identifier
- Sex
- Age
- AE as reported by the investigator
- PT term
- Time from first IP administration to AE onset
- Time from first IP administration to discontinuation of IP
- Seriousness
- Outcome
- Reasonable possibility AE caused by IP

Number and percentage of participants with AE of special interest by maximum reported toxicity grade will be summarised by study intervention group. A list of PT terms for AEs of special interest will be produced. Number of participants with AE for each medical concept (injection site reaction (ISR), serious hypersensitivity, serious infection, progression of heart failure, gastrointestinal adverse reactions, COVID-19) by maximum reported toxicity grade will be summarised by study intervention group.

Number of subjects with COVID-19 related AEs of special interest by SOC and PT will be summarised by treatment group and for total MEDI3506. Similar table will be repeated for the number of subjects with COVID-19 related serious AEs of special interest.

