TLF number	Title	Standard mock shell reference	Additional Information	Analysis1 (Week 12)	Analysis2 (Week 28)	Final Analysis
Table 14.3.2.5	Number of adverse events, by system organ class and preferred term (As-treated population)	AZ Corporate CSR/HLD Table Template S16(i)		X	X	X
Table 14.3.2.6	Number of subjects with adverse events, most common (frequency of >5%), by preferred term (As-treated population)	AZ Corporate CSR/HLD Table Template S8	Specify the period/periods which AE will be reported for, in the footnote Number (%) of subjects with AEs, sorted in decreasing frequency for preferred term (sorted by MEDI3506 treatment group) The cut off used is to be clearly stated in the title and footnote. The difference between S8 and FDAAA1 is – in S8 most common are defined as % in Total group, not individual treatment groups – and in FDAAA1 it is % in any treatment group.	X	X	X
Table 14.3.2.7	Non-serious adverse events occurring in greater than 5% of subjects (As-treated population)	AZ Corporate CSR/HLD Table Template FDAAA1		X	X	X
Table 14.3.2.8	Number of subjects with adverse events, by preferred term and maximum reported toxicity grade (As-treated population)	AZ Oncology CSR/HLD Table Template TAE050 - TA specific version of AZ Corporate CSR/HLD Table Template S10	Specify the period/periods which AE will be reported for, in the footnote Each subject has only been represented with the maximum reported toxicity grade for each preferred term. Subjects with events in more than 1 preferred term are counted once in each of those preferred terms. Each subject is counted only once (by their maximum reported toxicity grade) within a treatment group in this overall summary.	X	X	X

TLF number	Title	Standard mock shell reference	Additional Information	Analysis1 (Week 12)	Analysis2 (Week 28)	Final Analysis
Table 14.3.2.9	Number of subjects with adverse events, by preferred term and relationship as assessed by investigator (As- treated population)	AZ Corporate CSR/HLD Table Template S11	< <event rate="">> will not be included.</event>	X	X	X
Table 14.3.2.10	Number of subjects with adverse events, leading to dose interruption of IP, by system organ class and preferred term (As-treated population)	AZ Corporate CSR/HLD Table Template S_T1		X	X	X
Table 14.3.2.11	Number of subjects with COVID-19 related adverse events by system organ class and preferred term (As- treated population)	AZ Corporate CSR/HLD Table Template S9(i)		X	X	X

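### Two sentences in SAP 4.2.10.1 limit the COVID-19 tables by SOC and PT to adverse events of special interest, a limit that the endpoint, the SAP's own definition and Appendix A do not have

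*SAP*

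**What the plan says.** SAP 4.2.10.1 plans three dedicated COVID-19 summaries.

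- By toxicity grade: participants with an AE in each of several medical concepts. The list of concepts ends "progression of heart failure, gastrointestinal adverse reactions, COVID-19) by maximum reported toxicity grade will be summarised by study intervention group", and COVID-19 stands there as its own concept beside serious infection.
- By SOC and PT, all grades of seriousness: "Number of subjects with COVID-19 related AEs of special interest by SOC and PT will be summarised by treatment group and for total MEDI3506".
- By SOC and PT, serious events: "Similar table will be repeated for the number of subjects with COVID-19 related serious AEs of special interest".

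The safety endpoint in protocol Table 5 applies to participants who test positive for SARS-CoV-2 and is "the number and proportion of participants with COVID-19 AEs/SAEs and the proportion asymptomatic". SAP Table 4 repeats it with one word changed: "the number and proportion of patients with COVID-19 AEs/SAEs and the proportion asymptomatic".

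SAP 3.8.1, under its COVID-19 subheading, requires a positive nucleic acid or serology test during intervention or follow-up in a participant who "had an AE or SAE associated with COVID-19 based on the COVID-19 SMQ".

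Appendix A Table 14.3.2.11 is titled "Number of subjects with COVID-19 related adverse events by system organ class and preferred term". Table 14.3.4.1.3 is its counterpart for serious events.

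**The concern.** The two SOC/PT sentences add a condition that appears nowhere else in the chain from endpoint to definition to output. The condition is also hard to apply. The list of events of special interest in SAP 3.8.1 (the same as in protocol 8.3.6) does not name COVID-19. Its nearest entry opens "Serious infections (including opportunistic infections and viral reactivations", so on a plain reading a mild COVID-19 case does not qualify.

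The topic matters for safety: protocol 2.3.1 names serious infections, including those with SARS-CoV-2, as a potential risk of MEDI3506. At stake is whether the SOC/PT table delivers the AE part of the stated endpoint, and whether a programmer working from the text and one working from Appendix A would produce the same table.

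**Working it through.** The documents give no COVID-19 rate and the plan states no figure to reproduce, so the check is a comparison of texts.

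**Step 1. Which places carry a limit to events of special interest?**

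| Place | What is counted | Limit? |
|---|---|---|
| Protocol Table 5, SAP Table 4 | COVID-19 AEs/SAEs in participants testing positive | No |
| SAP 3.8.1, COVID-19 definition | Positive test plus COVID-19 SMQ | No |
| Appendix A, Table 14.3.2.11 | COVID-19 related AEs by SOC and PT | No |
| Appendix A, Table 14.3.4.1.3 | COVID-19 related SAEs by SOC and PT | No |
| SAP 4.2.10.1, toxicity-grade sentence; Table 14.3.6.8 | AEs under the COVID-19 concept, by maximum grade | No |
| SAP 4.2.10.1, the two SOC/PT sentences | COVID-19 related AEs, and serious AEs, of special interest | **Yes** |

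Only the last row differs. By wording, two of the three COVID-19 tables in 4.2.10.1 are limited. None of the three matching Appendix A tables is, and the visible part of Appendix A has no SOC/PT table of COVID-19 events of special interest.

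**Step 2. Could the limit be harmless because COVID-19 is itself of special interest?** SAP 3.8.1 lists seven categories: Hy's law liver abnormality, serious hypersensitivity, injection site reactions, cardiac events, serious infections, gastrointestinal events and malignancy. COVID-19 is not one of them, so the list does not make the limit harmless.

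**Step 3. Is it a declared change?** SAP Section 6 sets out the departures from the protocol analysis. Narrowing the COVID-19 endpoint is not among them.

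**Step 4. What would a literal reading remove, and from where?**

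- SOC/PT table of COVID-19 AEs: loses non-serious events that are not classed as of special interest.
- SOC/PT table of serious COVID-19 AEs: excludes non-serious events by design, so the limit removes none of those.
- Toxicity-grade table (14.3.6.8): loses nothing; it is presented by arm with no seriousness condition.
- General AE tables (for example 14.3.2.4 by SOC and PT, 14.3.2.8 by PT and grade) and the AE listings: lose nothing.

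So non-serious cases leave at most one table.

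**The case against.** The strongest reply is that this is loose wording which the output list already puts right. The SAP groups COVID-19 with the medical concepts of special interest in 4.2.10.1, and Table 14.3.6.8 sits in the block of special-interest outputs, so the author may have meant all COVID-19 events. The reference to a total for MEDI3506, in a trial with one active arm, suggests carried-over text. The SAP amendment history, useful here only as evidence of intent, records the addition of COVID-19 related AE tables without mentioning a limit. This reply is persuasive about intent. It does not remove the mismatch, because the body text still states a rule that the rest of the plan contradicts.

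A reader might infer three stronger things, and the documents support none of them.

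- *All COVID-19 tables are limited.* The sentence directly before the quoted one plans a COVID-19 table with no such limit.
- *Most cases leave the comparison between arms.* Non-serious cases stay, by arm, in Table 14.3.6.8 and in the general AE tables. It is fair to add that the toxicity-grade table has no SOC/PT breakdown and that the general tables do not apply the test-plus-SMQ definition. Neither therefore fully replaces the table in question.
- *A large, quantifiable share of events is lost.* Any percentage would only be one minus an assumed serious fraction. It would also treat *of special interest* as meaning *serious* for COVID-19 terms. SAP 3.8.1 does not settle that: the category is assigned by an investigator checkbox, cross-checked against SMQs and a term list that the patient safety team is still to supply, and some listed categories have no seriousness condition.

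**Conclusion.** The two sentences are wrong as written and the matter is minor. They contradict the safety endpoint, the SAP 3.8.1 definition and Appendix A Tables 14.3.2.11 and 14.3.4.1.3, which all agree with one another.

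The effect is confined to one descriptive SOC/PT table. It arises only if the text is followed literally in preference to Appendix A, and only for non-serious COVID-19 events that the checkbox and term list do not class as of special interest. The number of such events cannot be estimated from the documents. Data collection, the primary analysis and multiplicity control are unaffected.

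**What to change.** In SAP 4.2.10.1, delete the words *of special interest* from both COVID-19 SOC/PT sentences, and refer to the SAP 3.8.1 definition of COVID-19 related AEs and SAEs. The text then matches the endpoint and Tables 14.3.2.11 and 14.3.4.1.3. The mention of a total for MEDI3506 can go in the same edit, since there is one active arm.

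An alternative is to state in SAP 3.8.1 that COVID-19 is handled as a category of special interest regardless of seriousness. That is less economical: it would depart from the list in protocol 8.3.6 and change what counts as any event of special interest in the overview table.

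The cost is three words in each of two sentences plus a cross-reference. It needs no new data and no change to Appendix A.

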#### 4.2.10.2 Analysis of vital signs

Observed values and change from baseline in vital signs will be summarised by study intervention group and visit. Key participant information will be produced for vital sign parameters treatment-emergent changes outside predefined criteria (Table 23). All vital signs will be listed.

#### 4.2.10.3 Analysis of laboratory measurements

Laboratory evaluations (continuous haematology, clinical chemistry, urinalysis and coagulation results as per Table 22) will be summarised with descriptive statistics at each visit and change from baseline summarised for each post-baseline visit. Categorical urinalysis results will be summarised in shift tables comparing maximum value during treatment to baseline value. Shifts from baseline to maximum value during treatment in haematology, clinical chemistry, urinalysis and coagulation results will be presented using low, normal and high categories. Laboratory measurements will also be summarised based on the number and percentage of participants above or below a pre-specified threshold for each test, and a listing on key participant information supporting the summary will be provided.

Continuous haematology, clinical chemistry, urinalysis and coagulation results baseline versus maximum observation on treatment will be presented in figures using shift plots.

In addition to the summaries above also the maximum on-treatment ALT and AST by maximum total bilirubin for assessing Hy's law criteria will be presented using the following categories:

Liver Function Parameters	Category
	• $\geq 3 \times - < 5 \times ULN$
ALT	• $\geq 5 \times - <10 \times \text{ULN}$
	• $\geq 10 \times \text{ULN}$
	• $\geq 3 \times - < 5 \times \text{ULN}$
AST	• $\geq 5 \times - <10 \times \text{ULN}$
	• $\geq 10 \times ULN$
T = 4 = 1 1 ; 11;1 ;	• $<2 \times ULN$
l otal bilirubin	• $\geq 2 \times \text{ULN}$
Potential Hy's law	• (AST $\ge$ 3 × ULN or ALT $\ge$ 3 × ULN) and (Total Bilirubin $\ge$ 2×ULN) a

Fable 25	Category for Liver Function parameters
----------	---

ULN: upper limit of normal range.

a: It includes all subjects who have ALT or AST $\ge$ 3xULN and total bilirubin  $\ge$ 2xULN, and in which the elevation in transaminases precede or coincide with (that is, on the same day as) the elevation in total bilirubin.

ALT or AST versus total bilirubin, expressed as multiples of ULN as well as liver biochemistry test results over time – participants with elevated ALT or AST, and elevated total bilirubin will be presented in figures. Liver biochemistry results over time will be presented in figures for participants with elevated AST or ALT, and elevated total bilirubin. A separate listing of key information for participants with potential Hy's law will be produced.

All laboratory results will be listed.

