## 6.3.2 Methods to Ensure Blinding

Participants will be randomly assigned in a 1:1 ratio to receive study intervention (MEDI3506 or placebo). Investigators will remain blinded to each participant's assigned study intervention throughout the course of the study.

Since MEDI3506 and placebo are not identical, study intervention will be handled by an unblinded study intervention manager at the site and will be administered by an unblinded study team member who will not be involved in the management of study participants. An independent study intervention monitor will also be unblinded to perform study intervention accountability. In the event that the study intervention allocation for a participant becomes known to the investigator or other study staff involv. In the management of study participants, AstraZeneca must be notified *immediately*. The study intervention allocation for a participant needs to be known to treat an individual participant for an AE (Section 6.3.3), the investigator must notify AstraZeneca *immediately*. The site will maintain a written plan detailing which staff members are blinded/unbinded and the process of study intervention preparation and administration used to maintain. The blind.

In the event of a Quality Assurance audit the auditor(s) will be allowed access to unblinded study intervention records at the site(s) to verify that randomization/dispensing has been done accurately.

To facilitate the in-stream analysis of K and ADA samples, the randomisation schedule may be provided to limited person of who have responsibility for analysing the samples. These unblinded sample analysis will not have any other involvement with the conduct of the study.

MEDI3506 could reduce cosinophil counts in blood over time. As a precaution, eosinophil, basophil, and monocyte data from the hematology laboratory tests will not be communicated to blinded sponsor or site personnel during the intervention and follow-up periods. These data do not require blinding at baseline (SV1 to SV3 pre-dose).

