### 3.8.2 Laboratory variables

Following haematology, clinical chemistry, urinalysis and coagulation parameters will be assessed:

Haematology/haemostasis (whole blood a )	Clinical chemistry (serum)		
B-Haemoglobin (Hb)	S-Creatinine		
B-Leukocyte count	S-Bilirubin, total		
B-Leukocyte differential count (absolute count)	S-ALP		
B-Platelet count	S-AST		
B-Haematocrit	S-ALT		
B-Red blood cell count (RBC)	S-Albumin		
Urinalysis	S-Potassium		
U-Appearance and Color	S-Sodium		
U-Specific gravity	S-GGT		
U-Hb/Erythrocytes/Blood	S-Blood urea nitrogen		
U-Glucose	S-Total Protein		
U-Ketones	S-HbA1c		
U-pH	S-NT-ProBNP		
U-Bilirubin	S-Tryptase (only to be taken in event of suspected anaphylaxis see CSP Appendix I)		
U-Leukocytes	CCI		
U-Protein			
Microscopy including white blood cell/RBC and casts			
Pregnancy test (dipstick- urine human chorionic gonadotropin) as per SoA; NOTE: additional timepoint for female participants of CT sub-study			
Coagulation			
CCI	Activated partial thromboplastin time (APTT)		
Prothrombin International normalised ratio (INR)	Prothrombin Time		
a Whole blood samples will be collected concurrently for both haematology CC			

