Table 14.3.6.3	Number of subjects with adverse events of ISR, by maximum reported toxicity grade (As-treated population)	AZ Corporate CSR/HLD Table Template AS8		X	X	X
Table 14.3.6.4	Number of subjects with adverse events of serious hypersensitivity, by maximum reported toxicity grade (As-treated population)	AZ Corporate CSR/HLD Table Template AS8		X	X	X

TLF number	Title	Standard mock shell reference	Additional Information	Analysis1 (Week 12)	Analysis2 (Week 28)	Final Analysis
Table 14.3.6.5	Number of subjects with adverse events of serious infection, by maximum reported toxicity grade (As- treated population)	AZ Corporate CSR/HLD Table Template AS8		X	X	x
Table 14.3.6.6	Number of subjects with adverse events of progression of heart failure, by maximum reported toxicity grade (As-treated population)	AZ Corporate CSR/HLD Table Template AS8		X	X	X
Table 14.3.6.7	Number of subjects with adverse events of gastrointestinal adverse reactions, by maximum reported toxicity grade (As- treated population)	AZ Corporate CSR/HLD Table Template AS8		X	X	X
Table 14.3.6.8	Number of subjects with adverse events of COVID- 19, by maximum reported toxicity grade (As-treated population)	AZ Corporate CSR/HLD Table Template AS8		X	X	X

TLF number	Title	Standard mock shell reference	Additional Information	Analysis1 (Week 12)	Analysis2 (Week 28)	Final Analysis
Table 14.3.7.1.1	Haematology laboratory variables over time (As- treated population)	AZ Corporate CSR/HLD Table Template S25 (applied to Laboratory Data)	Choose timepoints relevant to the study: SV1, SV3, SV5, SV6, SV8, SV10, SV12, SV13, SV14, E/D Labels as per SAP Analysis Visit Windows. Report summary statistics Include Q1 and Q3 Include in the summary all haematology and clinical chemistry parameters listed in the protocol.	X	X	X
Table 14.3.7.1.2	Clinical chemistry laboratory variables over time (As-treated population)	AZ Corporate CSR/HLD Table Template S25 (applied to Laboratory Data)	Choose timepoints relevant to the study: SV1, SV3, SV5, SV6, SV8, SV10, SV12, SV13, SV14, E/D Labels as per SAP Analysis Visit Windows. Report summary statistics Include Q1 and Q3 Include in the summary all clinical chemistry parameters listed in the protocol.	X	X	X

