Table 14.3.7.1.3	Urinalysis laboratory variables over time (As- treated population)	AZ Corporate CSR/HLD Table Template S25 (applied to Laboratory Data)	Choose timepoints relevant to the study: SV1, SV3, SV5, SV6, SV8, SV10, SV12, SV13, SV14, E/D Labels as per SAP Analysis Visit Windows. Report summary statistics Include Q1 and Q3 Include in the summary all clinical chemistry parameters listed in the protocol.	X	X	X

TLF number	Title	Standard mock shell reference	Additional Information	Analysis1 (Week 12)	Analysis2 (Week 28)	Final Analysis
Table 14.3.7.1.4	Coagulation laboratory variables over time (As- treated population)	AZ Corporate CSR/HLD Table Template S25 (applied to Laboratory Data)	Choose timepoints relevant to the study: SV1, SV3, SV5, SV6, SV8, SV10, SV12, SV13, SV14, E/D Labels as per SAP Analysis Visit Windows. Report summary statistics Include Q1 and Q3 Include in the summary all clinical chemistry parameters listed in the protocol.	X	X	X
Table 14.3.7.2.1	Haematology laboratory variables, baseline versus maximum observation on treatment (As-treated population)	AZ Corporate CSR/HLD Table Template S27	Define baseline measurement in the footnotes	X	X	X
Table 14.3.7.2.2	Clinical chemistry laboratory variables, baseline versus maximum observation on treatment (As-treated population)	AZ Corporate CSR/HLD Table Template S27	Define baseline measurement in the footnotes	X	X	X
Table 14.3.7.2.3	Urinalysis laboratory variables, baseline versus maximum observation on treatment (As-treated population)	AZ Corporate CSR/HLD Table Template S27	Define baseline measurement in the footnotes	X	X	X
Table 14.3.7.2.4	Coagulation laboratory variables, baseline versus maximum observation on treatment (As-treated population)	AZ Corporate CSR/HLD Table Template S27	Define baseline measurement in the footnotes	X	X	X

TLF number	Title	Standard mock shell reference	Additional Information	Analysis1 (Week 12)	Analysis2 (Week 28)	Final Analysis
Table 14.3.7.4	Maximum on-treatment ALT and AST by maximum total bilirubin for assessing Hy's Law criteria (As-treated population)	AZ Corporate CSR/HLD Table Template AS14		X	X	X

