Table 14.3.7.5	Subjects with potential Hy's Law - individual subject data (As-treated population)	AZ Corporate CSR/HLD Table Template S32	"If there are subjects who met the criteria specified. A potential Hy's Law case is defined as any situation where a study subject has an increase in both AST or $ALT \ge 3 \times ULN$ and $TBL \ge 2 \times ULN$ , irrespective of ALP, at any point during the study." Multiple of ULN is defined as value divided by ULN, i.e. if the ALT value was X (ULN = Y) then the multiple would be X/Y.	X	X	X
Table 14.3.7.6	Urinalysis, baseline versus maximum observation on treatment, shift table (As- treated population)	AZ Corporate CSR/HLD Table Template S33	Define baseline measurement in the footnotes	X	X	X
Figure 14.3.7.1	Haematology laboratory variables, baseline versus maximum observation on treatment – shift plot (As- treated population)	AZ Corporate CSR/HLD Figure Template S8			X	X
Figure 14.3.7.2	Clinical chemistry laboratory variables, baseline versus maximum observation on treatment – shift plot (As-treated population)	AZ Corporate CSR/HLD Figure Template S8			X	X

TLF number	Title	Standard mock shell reference	Additional Information	Analysis1 (Week 12)	Analysis2 (Week 28)	Final Analysis
Figure 14.3.7.3	Urinalysis laboratory variables, baseline versus maximum observation on treatment – shift plot (As- treated population)	AZ Corporate CSR/HLD Figure Template S8			X	X
Figure 14.3.7.4	Coagulation laboratory variables, baseline versus maximum observation on treatment – shift plot (As- treated population)	AZ Corporate CSR/HLD Figure Template S8			X	x
Figure 14.3.7.5	ALT versus total bilirubin, expressed as multiples of ULN (As-treated population)	AZ Corporate CSR/HLD Figure Template S9	This must be produced for both ALT and AST. Also, that the preferred approach for the plot is that it should be produced on the log scale, and reference lines must be included at 2xULN for total bilirubin and at 3xULN for ALT/AST. Reference lines at 3*ULN of ALT /AST and 2*ULN for total bilirubin are compulsory Multiple of ULN is defined as value divided by ULN, i.e. if the ALT value was X (ULN = Y) then the multiple would be X/Y. Additional reference lines must be easily identified	X	X	X

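### Laboratory shift tables and plots use only the maximum on-treatment value, so a participant counts as low only if every on-treatment value is low

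*SAP*

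**What the plan says.** SAP 4.2.10.3 sets one rule for all four laboratory panels: "Shifts from baseline to maximum value during treatment in haematology, clinical chemistry, urinalysis and coagulation results will be presented using low, normal and high categories". For continuous parameters it adds that the "results baseline versus maximum observation on treatment will be presented in figures using shift plots".

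Appendix A carries this through. The title of Table 14.3.7.2.1 begins "Haematology laboratory variables, baseline versus maximum observation on treatment (As-treated population", and Tables 14.3.7.2.2 to 14.3.7.2.4 use the same form for clinical chemistry, urinalysis and coagulation. Figures 14.3.7.1 to 14.3.7.4 are each described as "baseline versus maximum observation on treatment – shift plot". No baseline-versus-minimum laboratory output is listed.

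The parameters in scope (SAP 3.8.2, Table 22) include haemoglobin, haematocrit, red cells, leukocytes, the "B-Leukocyte differential count (absolute count"), platelets, albumin, total protein, sodium and potassium.

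Section 4.2.10.3 also plans by-visit descriptive statistics, counts of participants outside preset limits for each test with a supporting listing, and a listing of all results. Protocol 9.4.3 makes the same commitment to threshold counts.

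**The concern.** For ALT, bilirubin or creatinine the maximum is the value of concern. For haemoglobin, white cells, platelets and albumin the value of concern is often the minimum, and for sodium and potassium it can be either. A low/normal/high table built on the maximum has a low column that is almost unreachable for these tests.

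The SAP attends to direction elsewhere. The ECG interpretation table in 4.2.10.4 equates the maximum with the worst category on an ordered scale, and vital signs in 3.8.3 are flagged in both directions. Section 3.1.5 refers to a minimum value when it brings in early-discontinuation and unscheduled data, yet no laboratory shift output uses one.

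At stake is the descriptive safety comparison. A reader of the shift tables could see no movement to low in either arm and take that as evidence that counts did not fall. No hypothesis test or estimand is affected.

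**Working it through.** The plan gives no figure of its own to reproduce, because this is an output rule. The check has a logical part and an illustration.

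**Logic.** For on-treatment values x1 to xk and lower limit L, max(x1..xk) < L if and only if every xi < L. By contrast, min(x1..xk) < L if at least one xi < L. A participant who is low at four of five visits and normal at the fifth is tabulated as normal under the maximum rule. With assumed haemoglobin values of 13.5, 13.2, 7.8, 12.9 and 13.1 g/dL, the table and the plot would use 13.5, and the fall to 7.8 would not be visible in them. In the plots, a point drops below the line of identity only if every on-treatment value is below baseline, and it enters the low range only if every value is low.

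**Number of values.** For haematology and chemistry, Appendix A gives: "Choose timepoints relevant to the study: SV1, SV3, SV5, SV6, SV8, SV10, SV12, SV13, SV14, E/D". SV1 and the pre-dose SV3 sample precede treatment. SAP 3.1.7 ends the on-treatment phase 28 days after the last dose. The last planned dose is at Day 169, and 169 + 28 = 197, the nominal day of SV12. The scheduled on-treatment values are therefore SV5, SV6, SV8, SV10 and SV12, so k = 5.

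**Illustration.** The per-visit probability p of a low value and the within-person correlation rho are assumptions, since neither document gives them. For independent values, P(low by maximum) = p^5 and P(low by minimum) = 1 − (1 − p)^5. With p = 0.10 these are 0.1^5 = 0.001% and 1 − 0.9^5 = 41.0%. For correlated values, one million draws of five equicorrelated normal values were simulated.

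| p | rho | Low by maximum | Low by minimum |
|---|---|---|---|
| 0.05 | 0 | 0.00003% | 22.6% |
| 0.05 | 0.5 | 0.15% | 16.6% |
| 0.05 | 0.8 | 1.1% | 11.6% |
| 0.10 | 0 | 0.001% | 41.0% |
| 0.10 | 0.5 | 0.58% | 29.2% |
| 0.10 | 0.8 | 2.8% | 20.9% |
| 0.20 | 0 | 0.03% | 67.2% |
| 0.20 | 0.5 | 2.4% | 48.7% |
| 0.20 | 0.8 | 7.4% | 36.6% |

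With 72 participants in an arm, p = 0.10 and rho = 0.8, the maximum would show about 72 × 0.028 = 2 participants as low and the minimum about 72 × 0.209 = 15.

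**Other outputs.**
- *By-visit tables.* SAP 4.1 requires quartiles, minimum and maximum, so the lowest value and the largest fall appear per arm and visit. They do not say how many participants moved from normal to low.
- *Threshold counts.* Apart from the liver categories in Table 25, the SAP states no laboratory limits. In the text available, Appendix A runs from Table 14.3.7.2.4 to 14.3.7.4 with no threshold table.
- *Listings.* They hold every value but are not a summary by arm. The individual laboratory listings are marked for the Week 28 and final analyses only, whereas the maximum-based shift tables are marked for all three.

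**The case against.** The strongest reply is that falls are covered elsewhere. The by-visit tables show minima and quartiles, the plan commits to counting values below a limit, and all results are listed. Protocol 8.3.5 makes clinically relevant laboratory deteriorations reportable as adverse events, which are tabulated by arm, and an unblinded DSMB reviews safety data. Much of this stands. A reader might infer that falls would appear nowhere in the report, and the documents do not support that. What remains missing is a by-arm count of participants who shifted to low. The threshold summary could supply it, but its haematology and albumin limits are unstated and its table is not listed. The number 14.3.7.3 is skipped and may have been lost in text extraction. If the sponsor's copy contains that table, only the missing limits remain on this part.

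A reader might also infer that the protocol expects white cells to fall and ties this to infection. It does not. Protocol 6.3.2 says only that the drug could lower eosinophils and withholds those data as a precaution. Table 4 bases the serious-infection risk on the role of IL-33, not on low counts. The redacted outputs may also include a separate eosinophil analysis.

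Finally, independence between repeated blood counts in one person is unrealistic. At p = 0.20 it gives 0.03% by maximum, against 2.4% to 7.4% with correlation 0.5 to 0.8. The range must therefore be shown, but the direction does not change.

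**Conclusion.** The point holds for the shift tables and shift plots. As specified, they do not count a participant as shifting to low unless every on-treatment value is low. That follows from the definition of a maximum and needs no assumption.

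The size is illustrative. With five values and an assumed 10% chance of a low value per visit, the maximum flags about 0.001% to 2.8% of participants and the minimum about 41% to 21%, for correlation 0 to 0.8. Even at the highest correlation the gap is more than sevenfold (20.9 / 2.8 ≈ 7.5).

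It would be tempting to conclude that the minimum should replace the maximum for blood counts. That goes too far: it would remove upward shifts in white cells and platelets from the tables, in a trial where serious infection is a named potential risk. This is a gap in descriptive safety reporting that is worth closing. It has no bearing on alpha, power or the efficacy analyses.

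**What to change.** Keep the existing maximum-based tables and plots. In SAP 4.2.10.3 and Appendix A, add baseline-to-minimum on-treatment shift tables and plots for:
- haemoglobin, haematocrit and red cells;
- leukocytes and each differential count;
- platelets;
- albumin and total protein;
- sodium and potassium.

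State the limits to be used for the threshold summary already promised in 4.2.10.3, and list its table in Appendix A, or confirm that it is listed under the skipped number.

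This needs no new data: the shift programs can be run again on the minimum. The cost is SAP wording and a few more output pages.
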